- Change from baseline in Continuity and Power of Attention, Working Memory, and Episodic Memory on the Cognitive Drug Research Computerized Cognition Battery (CDR-CCB).
- Change from baseline in Delis-Kaplan Executive Function System (D-KEFS) Verbal Fluency.
- Change from baseline in the Movement Disorder Society’s Unified Parkinson’s Disease Rating Scale (MDS-UPDRS) 1, 2, 3, and total score.
- Change from baseline in the Schwab and England Activities of Daily Living (SE-ADL) Scale.
- Change from baseline in the Clinical Impression of Severity Index – PD (CISI-PD).
- Change from baseline in the PD Quality of Life Questionnaire-39 (PDQ-39).
- Change from baseline in the Geriatric Depression Scale-15 (GDS-15).
- Change from baseline in the digital clock drawing test (dCDT).

Secondary Safety Endpoints:

- Change from baseline in clinical laboratory parameters.
- Change from baseline in vital sign measurements.
- Change from baseline in body weight.
- Change from baseline in the S-STS.

Exploratory Endpoints:

- Proteomic assessment of plasma for investigation of study-related biomarkers.
- Change from baseline in various MRI assessments (in consenting subjects).

Population:

Approximately 90 subjects between 40 and 85 years of age with a diagnosis of either PD with mild cognitive impairment (PD-MCI) or PD with dementia (PDD). Assuming a drop-out rate of 25%, enrollment at this level

will yield approximately 68 evaluable subjects.

Phase: 2

Number of Sites: Up to 40 sites in the US and ex-US

Description of Study

Agent: GRF6021: A [REDACTED] human [REDACTED] fraction for IV infusion

[figure not shown]
Description of
Placebo Control

Agent: 0.9% sodium chloride injection (saline)

Study Duration: Approximately 24 months

Subject Duration: Approximately 7 months

SCHEMATIC OF STUDY DESIGN

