- **Safety Set:** The Safety Set includes all subjects all subjects who receive at least 1 dose of the study agent. All safety analyses will be performed using the Safety Set, based on treatment received.
- **Intent-To-Treat Set (ITT):** The ITT Set includes all randomized participants. The presentation of baseline characteristics will be conducted on the ITT Set.
- **Evaluable Set:** The Evaluable Set includes all subjects who receive at least 5 of the 10 planned doses and complete through Visit 8. All efficacy analyses will be performed using the Evaluable Set, based on randomized treatment.
- **Per Protocol Set (PP):** The PP Set is a subset of the Evaluable set comprised of subjects who receive all 10 planned doses, who complete Visit 18 and Visit 19 in window, and who do not have any of the deviations listed below or any other deviation that could potentially affect the assessment of efficacy identified prior to database lock. Visit windows are found in Section 6.1.5. Deviations related to novel coronavirus disease 2019 (COVID-19) will also be evaluated in determining Per Protocol population eligibility prior to database lock. All efficacy analyses will be repeated in the Per Protocol Set, based on randomized treatment.
- **Complete Set:** The Complete Set is a subset of the PP Set comprised of subjects who did not have any changes to any of the following concomitant medications preferred terms reported at any time on study: Dopaminergic agents (e.g. Rotigotine [Neupro Patch], Duopa Pump, Sinemet [Carbidopa, Levodopa], Carbidopa, Rytary), Pregabalin (Lyrica), Amantadine, Antipsychotics (e.g. Pimavanserin Tartate [Nuplazid], Clozapine, Quetiapine Fumarate [Seroquel]), or benzodiazepines (e.g. Alprazolam). This includes those that were stable per protocol prior to first dose and either changed dose or stopped on study as well as those that began on study.

Deviation Type	Deviation	Major/Minor	Excluded from Per Protocol Set	Additional Clarification

Eligibility	I2. Diagnosis of clinically established or clinically probable PD according to MDS-PD criteria (Postuma 2015)(Appendix 8) with at least 1 year of PD symptoms	Major	Yes	
Eligibility	I3. Diagnosis of PD-MCI (Level I, i.e. impairment on a scale of global cognitive abilities validated for use in PD) or probable or possible PDD according to MDS criteria (Litvan 2012, Emre 2007)(Appendix 9)	Major	Yes	
Eligibility	I4. Score on the MoCA of 13-25, inclusive (Nasreddine 2005)(Appendix 1)	Major	Yes	

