- PDQ-39 Emotional Well-Being subscore = sum of 6 items in the Emotional Well-Being domain (converted from a range of 0 [never] to 4 [always/cannot do at all] to a range of 0 to 100), divided by the maximum possible score on the scale and multiplied by 100.

- PDQ-39 Stigma subscore = sum of 4 items in the Stigma domain (converted from a range of 0 [never] to 4 [always/cannot do at all] to a range of 0 to 100), divided by the maximum possible score on the scale and multiplied by 100.
- PDQ-39 Social Support subscore = sum of 3 items in the Social Support domain (converted from a range of 0 [never] to 4 [always/cannot do at all] to a range of 0 to 100), divided by the maximum possible score on the scale and multiplied by 100.
- PDQ-39 Cognitions subscore = sum of 4 items in the Cognitions domain (converted from a range of 0 [never] to 4 [always/cannot do at all] to a range of 0 to 100), divided by the maximum possible score on the scale and multiplied by 100.
- PDQ-39 Communication subscore = sum of 3 items in the Communication domain (converted from a range of 0 [never] to 4 [always/cannot do at all] to a range of 0 to 100), divided by the maximum possible score on the scale and multiplied by 100.
- PDQ-39 Bodily Discomfort subscore = sum of 3 items in the Bodily Discomfort domain (converted from a range of 0 [never] to 4 [always/cannot do at all] to a range of 0 to 100), divided by the maximum possible score on the scale and multiplied by 100.
- PDQ-39 Total score = mean of all of the PDQ-39 subscores.
- GDS-15 Total score = sum of the 15 item questionnaire, with a range of 0 to 15. Each question is answered “yes” or “no”. Question numbers 1, 5, 7, 11, 13 indicate presence of depression when answered positively (yes) while the remaining questions indicate presence of depression when answered negatively (no). One point is counted for each depressive answer. A score of 0-4 indicates no depression, a score of 5-10 is suggestive of a mild depression, and a score of 11 or more is suggestive of severe depression.
- Modified Hachinski Ischemic Scale Total score = sum of the 8 item scores, with a range of 0-8.
- Change from baseline = value at current time point – value at baseline.
- TEAE = any adverse event with an onset date/time after first dose of medication.
- Disease duration (years) = [Enrollment date – PD onset date (as recorded on the Medical History case report form) + 1] / 365.25.

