9.1. Adverse Events

All AEs that occur after the time of treatment with the study agent will be considered TEAEs. Events meeting this definition will be those events that are a change from the subject's baseline conditions, including an increase in frequency or severity (these will be entered as new AEs). For AEs occurring on the date of first dose, if the time of onset is missing, the AE will be assumed to be treatment emergent.

All AEs, TEAEs, and SAEs will be coded using the MedDRA Version 20.1 or higher coding dictionary. The AE analyses will focus on those that are treatment emergent, however any AEs that are reported after consent has been signed and before initial dosing will be considered intercurrent events and flagged in the listings as such.

The causal relationship of the AE to the study drug is determined by the investigator as Unrelated, Possibly Related, or Definitely Related. These can be mapped to Unrelated (*Unrelated*) and Related (*Possibly Related* and *Definitely Related*). Adverse event summaries will be repeated for treatment related TEAEs.

Adverse events severity grades are reported as mild, moderate, or severe.

Summaries of incidence rates (frequencies and percentages) of individual TEAEs will be presented by SOC, PT, and treatment group. Such summaries will be displayed for all TEAEs, TEAEs by maximum severity, and TEAEs by relationship.

Each subject will be counted only once within each summation level (SOC and PT). If a subject experiences more than 1 TEAE within each summation level only, the TEAE with the strongest relationship or the maximum severity, as appropriate, will be included in the summaries of relationship and severity. If a particular event is missing the severity and/or relationship, then the strongest possible severity or relationship will be assumed for analysis (severity = severe, relationship = definitely related).

Incidences will be presented by descending frequency of SOC and PT within SOC, and then alphabetically within PT where the incidence is the same; this is based on overall subjects then alphabetically in case of a tie.

Missing and partially missing AE start and/or stop dates will be imputed, for the purpose of statistical analysis, according to the specifications described in Section 6.1.8.

In the AE data listings, all AEs will be displayed. AEs that are treatment emergent will be flagged.

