A test of hypothesis comparing the proportion of subjects reporting a TEAE throughout the study will be conducted using a Chi-square test or Fisher's exact test, as appropriate. The null hypothesis is that there is no difference in proportion between treatment groups, with a two-sided alternative that considers the possibility of a difference in either direction. The number and percentage of subjects reporting a TEAE and the 95% Wilson confidence interval (CI) for the proportion will be presented for each treatment group. In addition, the difference in proportions between the GRF6021 and placebo groups and the 95% Wilson CI will be presented. The same statistics and hypothesis testing will be performed for subjects reporting an SAE throughout the study.

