9.1.3. Other Significant Adverse Events

AEs of special interest (AESI) are defined in the protocol. These are to be considered as Adverse Events by the PI in order to be recorded:

A summary tabulating these criteria for safety will be presented by SOC, PT, and treatment group. All AESIs will be flagged in the AE listings.

Adverse events with preferred terms associated with blood pressure changes will also be presented by infusion period, SOC, PT, and treatment group. Infusion period will be further categorized by whether the event start date occurred during the infusion period or after the infusion period. Examples of such events can be identified by the following preferred terms: blood pressure decreased, blood pressure diastolic decreased, blood pressure systolic decreased, blood pressure increased, increased blood pressure, blood pressure diastolic increased, blood pressure systolic increased, hypotension, hypertension, low blood pressure, high blood pressure. This is a non-exhaustive list and a review of AE MedDRA coding will be conducted prior to lock to identify all events associated with blood pressure changes.

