System Organ Class 1			
Preferred Term 1 (Blood Pressure Decreased)	XX (XX.X%)	XX (XX.X%)	XX (XX.X%)
Preferred Term 2 (Blood Pressure Increased)	XX (XX.X%)	XX (XX.X%)	XX (XX.X%)
System Organ Class 2			
Preferred Term 1 (Blood Pressure Decreased)	XX (XX.X%)	XX (XX.X%)	XX (XX.X%)
Preferred Term 2 (Blood Pressure Increased)	XX (XX.X%)	XX (XX.X%)	XX (XX.X%)
Starting During Infusion Period 1			
System Organ Class 1			
Preferred Term 1 (Blood Pressure Decreased)	XX (XX.X%)	XX (XX.X%)	XX (XX.X%)
Preferred Term 2 (Blood Pressure Increased)	XX (XX.X%)	XX (XX.X%)	XX (XX.X%)
System Organ Class 2			
Preferred Term 1 (Blood Pressure Decreased)	XX (XX.X%)	XX (XX.X%)	XX (XX.X%)
Preferred Term 2 (Blood Pressure Increased)	XX (XX.X%)	XX (XX.X%)	XX (XX.X%)
Starting After Infusion Period 1			
System Organ Class 1			
Preferred Term 1 (Blood Pressure Decreased)	XX (XX.X%)	XX (XX.X%)	XX (XX.X%)
Preferred Term 2 (Blood Pressure Increased)	XX (XX.X%)	XX (XX.X%)	XX (XX.X%)
...			

Abbreviations: CRF = case report form; PT = preferred term; SOC = system organ class; TEAE = treatment emergent adverse event.
Note: Percentages are n/Number of subjects in the Safety Set*100. Subjects are summarized by treatment received. AEs were coded using MedDRA version 21.0 A TEAE is any AE that occurs after the time of treatment with the study agent. This will include any AE with onset prior to time of treatment with study agent and increased severity after the treatment administration. Subjects are counted once for each SOC and once for each PT. AEs are displayed by descending frequency of SOC, then PT within SOC, and then alphabetically by PT.
SOURCE: Listing 16.2.7.1

Programming Note: Continue for "Starting During Infusion Period 2" and "Starting After Infusion Period 2."

Statistical Analysis Plan,
Sponsor Alkermes, Inc.
Protocol Number ALK6021-201
PCN Number ALKA7951

Table 14.3.3.1
Listing of Adverse Events Leading to Study Drug Discontinuation
All Subjects

Subject ID	Treatment [1]	TEAE/ Intercurrent	System Organ Class/ Preferred Term/ Verbatim Term	Start Date (Study Day) Start Time / End Date (Study Day) End Time	Severity/ Relationship	Outcome/ Study Drug Action Taken (CRF)/ Other Action Taken	Derived Action Taken	Serious?/ Criteria Met	AESI? [2]

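### The Period 2 rows of SAP Table 14.3.2.4 divide by the whole Safety Set, so second-course blood-pressure AE incidence is understated by the fraction of subjects not re-dosed

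*SAP*

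**What the plan says.** SAP 9.1.3 provides one split of adverse events by course: "Adverse events with preferred terms associated with blood pressure changes will also be presented by infusion period, SOC, PT, and treatment group". Events are further divided by whether they start during or after the infusion period. The shell is Table 14.3.2.4, whose footnote reads "Percentages are n/Number of subjects in the Safety Set*100". The shell shows the Period 1 rows, and a programming note extends it to the second course: "Continue for 'Starting During Infusion Period 2' and 'Starting After Infusion Period 2". No other denominator is given for those rows.

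SAP Section 5 defines the population: "The Safety Set includes all subjects all subjects who receive at least 1 dose of the study agent". SAP 4.1 makes the total study population in each arm the general denominator. It allows a non-missing denominator only for by-visit displays, which these rows are not.

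For other events, SAP 9.1 states: "Summaries of incidence rates (frequencies and percentages) of individual TEAEs will be presented by SOC, PT, and treatment group". SAP 6.1.7 sets the window: "TEAE = any adverse event with an onset date/time after first dose of medication". Neither has a split by course.

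The Table 4 list in SAP 13.3 flags Table 14.3.2.4 for both the safety and the efficacy interim analyses.

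**The concern.** A subject who is never re-dosed cannot have an event during or after Period 2 dosing, yet is in the denominator of both rows. The plan expects such subjects. Protocol 10.4.5 compares subjects who complete both series with those who complete only the first. SAP 7.1 counts COVID-19 absences that affected treatment administration. Table 3 of the Infusion Administration Manual (Protocol Appendix 11) ends dosing after listed moderate-to-severe infusion events. That last route ties non-re-dosing to infusion harm, so it could differ between arms. The arm losing more subjects would then have its second-course percentage lowered more.

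Safety is the primary objective, and this is the only planned AE table that isolates the second course. A reader will take its percentages as incidence on re-dosing.

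**Working it through.** **Inputs.** About 60 active and 30 placebo subjects (SAP 3.2). Safety Set: at least one dose (SAP Section 5). Visit 8 is Day 6, Visit 11 is Day 85 and follow-up runs to Day 168 (Protocol Section 15). The proportion not starting course 2 is in neither document and is varied as an assumption. I assume a late event in a subject not re-dosed falls under the after-Period-1 row; the SAP does not say.

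**The plan's own figures.** Rule of threes: 3/60 = 5.0%, as stated. Evaluable subjects: 90 × (1 − 0.25) = 67.5, matching about 68.

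**Denominator effect.** Printed % = true % among the re-dosed × (re-dosed / Safety Set). With a true 20% and 60 active subjects:

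| Not re-dosed (assumed) | Re-dosed | Printed % | Rule-of-threes bound, course 2 |
|---|---|---|---|
| 5% | 57 | 19% | 3/57 = 5.3% |
| 10% | 54 | 18% | 3/54 = 5.6% |
| 15% | 51 | 17% | 3/51 = 5.9% |
| 25% | 45 | 15% | 3/45 = 6.7% |
| 40% | 36 | 12% | 3/36 = 8.3% |

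In the 25% row, 9 events are 9/45 = 20.0% of those at risk but print as 9/60 = 15.0%. Period 1 rows are unaffected, since every Safety Set subject started course 1.

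**Unequal non-re-dosing (assumed 25% active, 10% placebo).**
- Equal true 20%: 20 × 0.75 = 15% versus 20 × 0.90 = 18%, an apparent 3-point advantage for active.
- True 30% versus 15%: 22.5% versus 13.5%, a difference of 9 points instead of 15.
- With the loss rates reversed, equal true rates print as 18% versus 15%, so the direction depends on which arm loses more.

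**Interim looks.** Both are triggered by Visit 8 completion, 85 − 6 = 79 days before the second course. Protocol 10.4.7 says the safety look included 32 subjects; it does not say how many had started course 2. If 8, 12 or 16 had, the factor is 0.25, 0.375 or 0.50, and a true 20% prints as 5%, 7.5% or 10%.

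**Events other than blood pressure.** Let w be the infusion-time risk and b an independent background risk of the same term, equal in both arms. Whole-study incidence is 1 − (1 − w)(1 − b), so the arm difference shrinks by the factor (1 − b). For assumed w of 15% versus 5%:

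| b | Active | Placebo | Difference | Ratio |
|---|---|---|---|---|
| 0 | 15.0% | 5.0% | 10 points | 3.00 |
| 10% | 23.5% | 14.5% | 9 points | 1.62 |
| 20% | 32.0% | 24.0% | 8 points | 1.33 |
| 50% | 57.5% | 52.5% | 5 points | 1.10 |

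Terms with little background lose little; common terms lose much of the contrast.

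**The case against.** The Safety Set is the SAP's general convention, and events per treated subject is a valid quantity. The table is descriptive and untested, and it prints n and N. Table 14.1.1 gives visit and dosing-period completion by arm, Table 14.1.5 gives exposure by dosing period, and the AE listing gives onset date and time. A careful reader could rebuild the rate and see unequal non-re-dosing. All this limits the harm, but it does not make the printed figure an incidence on re-dosing.

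A further objection stands in full: the re-dosed are selected after randomisation. If poor tolerators skip course 2, the corrected percentages could make active look safer. The new denominator therefore needs a caveat.

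Four stronger readings are tempting but unsupported:

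- **That the protocol gives a 25% loss before the second course.** The Protocol Summary says "Assuming a drop-out rate of 25%, enrollment at this level" will yield about 68 evaluable subjects, and evaluability runs only through Visit 8. It is not a rate for failing to reach Visit 11.
- **That the second course is the only re-exposure.** Infusions 2 to 5 of course 1 are re-exposures too; course 2 is the only one after a long gap. Protocol 2.3.1 also says the product is not expected to sensitise recipients.
- **That the table will favour active.** This needs equal true rates and greater loss on active, neither of which the documents establish.
- **That infusion-day harm will be lost in the whole-study analysis.** SAP 9.1 does test "A test of hypothesis comparing the proportion of subjects reporting a TEAE throughout the study", a heavily diluted comparison, but the primary endpoint is by preferred term and organ class. Table 14.3.1.4 separates related events, and blood pressures of special interest are shown by within-infusion timepoint. No preferred-term tests are planned, so a power argument carries little weight.

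**Conclusion.** The concern holds for the two Period 2 rows of Table 14.3.2.4. Whenever a second-course event occurs and anyone in the arm was not re-dosed, the printed percentage is below the incidence among those re-dosed, by a relative amount equal to the fraction not re-dosed. Over an assumed 5% to 40%, a true 20% prints as 19% down to 12%. Distortion between arms follows only if non-re-dosing differs by arm; its size and direction here are illustrations. The effect would be greatest at the interim looks. Protocol 10.4.7 reports the safety look as done, but the documents do not show what its Period 2 rows contained.

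The absence of a course split for other events is a lesser point. It rests on Protocol 2.3.1 naming hypersensitivity as well as hypotension as an identified risk, while only blood-pressure terms are split.

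**What to change.** 1. In Table 14.3.2.4, divide both Period 2 rows by the subjects in each arm who received any study agent in Period 2 (at an interim, by the data cut). Print that N beside the Safety Set N.
2. Add a footnote that the re-dosed are a selected, non-randomised subset, so between-arm differences in these rows are descriptive.
3. State in SAP 9.1.3 where a late event in a subject not re-dosed is counted.
4. As a secondary addition, repeat Table 14.3.1.2 with the same during/after-course split and denominators.

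Items 1 to 3 cost a footnote, a second N and a sentence, with no new data: exposure by dosing period is already tabulated and AE onset times are recorded. Item 4 costs one more descriptive table.

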 4. MDS-UPDRS 1/2/3
 5. SE-ADL
 6. CISI-PD
 7. PDQ-39
 8. GDS-15

7.3.4 TREATMENT

There are two treatment periods scheduled during the trial. During each treatment period, subjects will receive a total of 5 infusions of their assigned treatment (i.e., either GRF6021 or placebo). It is anticipated that sites will infuse subjects with 5 doses over 5 consecutive days. A “grace day” is allowed in the event of unanticipated safety or health concerns during each treatment period.

Visits 3-7 (Days 1-5) and 11-15 (Day 85*-89):

*Day 85 has a \pm 7-day window

- Perform the following procedures prior to administering study treatment:
 - Review AEs and concomitant medications.
 - Obtain blood and urine samples for Comprehensive Labs (**Visits 6 and 14 Only**); fasting samples preferred.
 - Obtain samples for proteomics/epigenetics/biobanking; fasting samples preferred (**Visits 3 and 11 Only**).
 - Obtain sample for ApoE testing (**Visit 3 Only**).
 - For WOCBP Only: perform pregnancy testing and review results (**Visits 3 and 11 Only**).
 - Obtain Pre-infusion Safety Lab samples and assess results **prior to the next day’s infusion (Visits 3, 4, 6, 11, 12, and 14 Only)**. When using an i-STAT Handheld Blood Analyzer, the blood sample(s) may be obtained on the same day as the infusion (Visits 4, 5, 7, 12, 13, and 15).
 - Perform targeted physical exam (i.e. auscultation of heart and lungs and assessment of peripheral edema) (**Visits 3, 5, 7, 11, 13, and 15 Only**).
 - Measure body weight in kilograms.
 - Perform 12-lead ECG (**Visit 7, 11, and 15 Only**).
 - Administer the S-STS (**Visit 3 Only**).
 - Collect vital signs (including sitting, supine, and standing BP).
- Administer study treatment and perform safety assessments per the Infusion Administration Manual ([Appendix 11](#)).
- Administer the S-STS after the subject’s final infusion (**Visit 7 Only**).

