2.2.1.2. Secondary Safety Endpoints

The secondary safety endpoints include the following:

- Change from baseline in clinical laboratory parameters.
- Change from baseline in vital sign measurements.
- Change from baseline in body weight.
- Change from baseline in the S-STs.

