6.1. Statistical Definitions and Algorithms

6.1.1. Baseline

The last observation recorded before the first dose will be used as the baseline observation for all calculations of change from baseline.

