9.5.2. Sheehan-Suicidality Tracking Scale (S-STs)

The S-STs is a 16-item scale that assesses the seriousness of suicidality phenomena on a Likert-type scale (0-4) ranging from "not at all" (0) to "extremely" (4). It also assesses the frequency of key phenomena and the overall time spent in suicidality. This study is only collecting the total

scale score. S-STS total scores will be summarized descriptively by treatment and visit as both observed values and change from baseline values.

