Programming Note: Parameters include: *Sitting Systolic Blood Pressure (mmHg) and Sitting Diastolic Blood Pressure (mmHg). For Sitting Diastolic Blood Pressure, the categories will be: DBP < 50, DBP >110, DBP > 120, and at post baseline visits, CFB ≥ 30%*

Statistical Analysis Plan,
Sponsor Alkermes, Inc.
Protocol Number ALK6021-201
PCN Number ALKA7951

Table 14.3.6.2.1
Summary of 12-Lead Electrocardiogram by Study Visit and Treatment
Safety Set

(Same shell as Table 14.3.5.1.1; visits include Visit 1, Visit 7, Visit 11, and Visit 15; parameters include HR, QT, QTcF; SOURCE: Listing 16.2.8.3)

Statistical Analysis Plan,
 Sponsor Alkermes, Inc.
 Protocol Number ALK6021-201
 PCN Number ALKA7951

Table 14.3.6.2.2
 Summary of 12-Lead Electrocardiogram Interpretation by Study Visit and Treatment
 Safety Set

Study Visit Category	Placebo (N=XX) n (%)	GRF6021 (N=XX) n (%)	Overall (N=XX) n (%)
Baseline [1]			
Normal	XX (XX.X%)	XX (XX.X%)	XX (XX.X%)
Abnormal, Not Clinically Significant	XX (XX.X%)	XX (XX.X%)	XX (XX.X%)
Abnormal, Clinically Significant	XX (XX.X%)	XX (XX.X%)	XX (XX.X%)
Week 1 (Visit 7)			
Normal	XX (XX.X%)	XX (XX.X%)	XX (XX.X%)
Abnormal, Not Clinically Significant	XX (XX.X%)	XX (XX.X%)	XX (XX.X%)
Abnormal, Clinically Significant	XX (XX.X%)	XX (XX.X%)	XX (XX.X%)
Week 13 (Visit 11)			
Normal	XX (XX.X%)	XX (XX.X%)	XX (XX.X%)
Abnormal, Not Clinically Significant	XX (XX.X%)	XX (XX.X%)	XX (XX.X%)
Abnormal, Clinically Significant	XX (XX.X%)	XX (XX.X%)	XX (XX.X%)
Week 13 (Visit 15)			
Normal	XX (XX.X%)	XX (XX.X%)	XX (XX.X%)
Abnormal, Not Clinically Significant	XX (XX.X%)	XX (XX.X%)	XX (XX.X%)
Abnormal, Clinically Significant	XX (XX.X%)	XX (XX.X%)	XX (XX.X%)

Note: Percentages are n/Number of subjects in the Safety Set*100. Subjects are summarized by treatment received.
 [1] The baseline value for each variable is the value recorded prior to the first dose
 SOURCE: Listing 16.2.8.3

Table 14.3.6.3
Summary of Sheehan-Suicidality Tracking Scale (S-STs) by Study Visit and Treatment
Safety Set

Study Visit Statistic	Placebo (N=XX)		GRF6021 (N=XX)		Overall (N=XX)	
	Observed	CFB	Observed	CFB	Observed	CFB
Visit 1						
n	XX	XX	XX	XX	XX	XX
Mean (SD)	XX.X (XX.XX)	XX.X (XX.XX)	XX.X (XX.XX)	XX.X (XX.XX)	XX.X (XX.XX)	XX.X (XX.XX)
Median	XX.X	XX.X	XX.X	XX.X	XX.X	XX.X
Min, Max	XX, XX	XX, XX	XX, XX	XX, XX	XX, XX	XX, XX
Week 1 (Visit 3)						
n	XX	XX	XX	XX	XX	XX
Mean (SD)	XX.X (XX.XX)	XX.X (XX.XX)	XX.X (XX.XX)	XX.X (XX.XX)	XX.X (XX.XX)	XX.X (XX.XX)

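### The S-STS table labels no baseline, prints change at pre-dose visits, and gives no count by arm of subjects whose score rose after dosing

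*SAP*

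**What the plan says.** SAP 2.2.1.2 lists "Change from baseline in the S-STs" among the secondary safety endpoints. SAP 9.5.2 gives the analysis: "S-STS total scores will be summarized descriptively by treatment and visit", as observed values and as changes from baseline. The same section says that only the total scale score is collected.

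The baseline rule is general. SAP 6.1.1 states: "The last observation recorded before the first dose will be used as the baseline observation for all calculations of change from baseline".

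The scale is given at screening (Visit 1) and twice more. Protocol 7.3.4 lists the Visit 3 administration under the instruction "Perform the following procedures prior to administering study treatment", and places the Visit 7 administration after the infusion on that day, the last of the first dosing period.

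The shell for Table 14.3.6.3, titled "Summary of Sheehan-Suicidality Tracking Scale (S-STs) by Study Visit and Treatment", has rows for Visit 1, Week 1 (Visit 3) and Week 1 (Visit 7). Each row has observed and change columns for placebo, GRF6021 and overall, filled with n, mean (SD), median, and minimum and maximum. Its notes explain the abbreviation for change and say that subjects are summarised by treatment received. There is no row labelled as baseline and no baseline footnote. The laboratory, blood-pressure and ECG-interpretation shells in SAP 14.2 have both.

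**The concern.** There are two separate points.

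**Layout.** The table invites a change from baseline at two visits that both precede the first dose, and a programmer working from the shell alone has to go back to SAP 6.1.1 to find the baseline. Other parts of SAP 14 name Visit 1 as baseline in their footnotes (the SE-ADL table and the hematology listing), so a slip is conceivable.

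**Content.** For a suicidality scale in a safety trial, the natural question is how many subjects in each arm were worse after the infusions than before. A mean of total scores answers this poorly when most scores are 0, because rises and falls cancel and the median stays at 0. The minimum and maximum show the extremes but not the numbers. A reader of the S-STS table could not compare the arms on the proportion who worsened.

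**Working it through.** The plan states no figure for this endpoint, so there is none to reproduce. The check is a comparison of sections followed by a numeric illustration.

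**1. Which changes are post-dose.** Write S1, S3 and S7 for the total scores at Visits 1, 3 and 7. SAP 6.1.1 takes the last value before the first dose. Protocol 7.3.4 puts the Visit 3 S-STS before the infusion. Baseline is therefore S3, or S1 if S3 is missing. With S3 present, the shell's change cells become:

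| Row | Change | Meaning |
|---|---|---|
| Visit 1 | S1 − S3 | difference between two pre-dose scores |
| Visit 3 | S3 − S3 = 0 | zero for every subject |
| Visit 7 | S7 − S3 | the only post-dose change |

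Two of the three change blocks carry no information about treatment.

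**2. What the planned statistics can show.** Take n = 60, the planned active arm (SAP 3.2). The score changes below are assumed; the documents give no S-STS distribution. Changes not listed are 0. SD = √[(Σx² − (Σx)²/60)/59].

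| Case | Changes at Visit 7 | Mean | SD | Median | Min, max | Subjects with a rise |
|---|---|---|---|---|---|---|
| A | one at +8 | 8/60 = 0.13 | 1.03 | 0 | 0, 8 | 1 |
| B | two at +4 | 8/60 = 0.13 | 0.72 | 0 | 0, 4 | 2 |
| C | three at +4, three at −4 | 0 | √(96/59) = 1.28 | 0 | −4, 4 | 3 |
| D | one at +4, two at +2, eight at +1, four at −4 | 0 | √(96/59) = 1.28 | 0 | −4, 4 | 11 |

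A and B share a mean and median, but their SD and maximum differ. C and D agree on every statistic in the change column:

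- C: sum = 12 − 12 = 0; sum of squares = 6 × 16 = 96.
- D: sum = 4 + 4 + 8 − 16 = 0; sum of squares = 16 + 8 + 8 + 64 = 96; 60 − 15 = 45 subjects are unchanged, so the median is 0.

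The number who rose is 3 in C and 11 in D. The printed change statistics therefore do not determine it.

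**3. What a count would show.** In case C the added row would read 3/60 = 5.0%, exact (Clopper-Pearson) 95% CI 1.0% to 13.9%. In case D it would read 11/60 = 18.3%, exact 95% CI 9.5% to 30.4%. Set against 0/30 on placebo, 3/60 gives a Fisher exact p of 0.55. The count is a description and would rarely separate the arms by a test.

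**4. Whether the count appears elsewhere.** Listing 16.2.8.6 shows each subject's total score with treatment. The tables of treatment-emergent adverse events (SAP 9.1) count suicidality by preferred term and arm if it is reported as an adverse event. No summary table counts a score rise that was not so reported.

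**The case against.** The case against is substantial, and much of it stands.

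- **Baseline is defined.** A reader might infer from the shell that Visit 1 is the baseline, and so that the Visit 7 change includes drift during screening. The documents do not support that. SAP 6.1.1 covers all change calculations, a missing footnote does not override it, and the shell prints change cells in the Visit 1 row too, so the layout does not single out Visit 1. Table 14.3.5.1.1 also prints change cells in a row it labels as baseline, which suggests template filler. This part is a labelling inconsistency.
- **The table is not limited to means.** SD, median, minimum and maximum are printed by arm. In case C the reader would see −4 and 4 and know that at least one subject worsened, and by how much at most.
- **Suicidality is not left uncounted.** Events reported as adverse events are counted by arm, and with about 90 subjects anyone could tally rises from the listing. What is missing is an S-STS summary with a count.
- **The SAP follows the protocol.** Protocol 10.4.4 names the S-STS score among the continuous safety endpoints and lists the same statistics. Leaving out a count breaches no stated plan.
- **The gain is limited.** With only the total score collected, ideation and behaviour cannot be separated. Visit 7 is the only post-dose administration in Protocol 7.3.4, so a count covers the first dosing week only.

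None of this supplies the count, and the SAP already tabulates subject counts by arm for blood pressures of special interest, laboratory shifts and ECG interpretation.

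**Conclusion.** The point holds in a limited form. Table 14.3.6.3 is not aligned with SAP 6.1.1: it labels no baseline and prints change at two pre-dose visits. Separately, no planned S-STS table says how many subjects per arm had a higher score after dosing, and the planned statistics do not determine that number. A rise not reported as an adverse event enters no summary count.

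The size depends on the score distribution, which the documents do not give. The illustration assumes that most subjects have no change. On that assumption, 3 and 11 rises among 60 can print identically. If scores were spread widely, the mean and SD would be more informative, though the count would still be absent.

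This is a cheap improvement to a named secondary safety endpoint. It does not show that the endpoint is wrongly defined, that its baseline is unknown, or that suicidality would go unrecorded.

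**What to change.** In SAP 9.5.2 and Table 14.3.6.3:

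1. Label the Visit 3 pre-infusion score as the baseline, with Visit 1 used if Visit 3 is missing, and add the baseline footnote used in the other safety shells.
2. Print change from baseline only at Visit 7. Visit 1 can stay as an observed value.
3. Add by arm the n (%) with total score above 0 at each visit, and the n (%) with an increase from baseline at Visit 7, with 95% CIs. Use subjects with both scores as the denominator for the increase.
4. While editing, correct the source reference: the shell cites Listing 16.2.8.5, but the S-STS listing is 16.2.8.6.

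The cost is a shell edit and a few rows computed from the total score already collected. The downside is small counts with wide intervals, limited to the first dosing week; a footnote should say so.
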